4.3 Other Considerations

Participants meeting any of the following criteria may have planned study vaccination deferred for a later date, but these criteria are not exclusionary for study enrolment.

- Respiratory symptoms in the past 3 days (i.e., cough, sore throat, difficulty breathing). Participant may be vaccinated once all symptoms have been resolved for > 3 days. Out-of-window study vaccination is allowed for this reason (see NOTE).
- Temperature of > 38°C within 24 hours of planned study vaccination (site measured or participant measured). Participant may be vaccinated once the fever has resolved and there has not been any temperature measured as being > 38°C for > 3 days. Out-of-window study vaccination is allowed for this reason (see NOTE).

NOTE: PCR testing for SARS-CoV-2 is likely to be indicated for either of the above reasons or if COVID-19 is suspected based on other symptoms, potential exposure to SARS-CoV-2 infection through either close contacts or based on local epidemiology. If a participant has a positive PCR for SARS-CoV-2 prior to enrolment that participant will not be eligible and will be considered a screen failure.

- Participants having any symptoms or signs of possible COVID-19 infection (Table 2-2) that may also be due to post-vaccination reactogenicity within 7 days of either study vaccine dose will NOT be required to be tested for SARS-CoV-2 PCR.
- Any participant with a new positive PCR-confirmed SARS-CoV-2 infection occurring from Screening and prior to second study vaccination will not be removed from the study but must meet health requirements before receiving the second study vaccination.
- Any participant who has a positive PCR for SARS-CoV-2 between the first and second study vaccination should also have PCR testing for SARS-CoV-2 on the day of the subsequent study vaccination, but the results of the PCR test are not needed before study vaccination can be given.
- Any participant with a new positive PCR-confirmed SARS-CoV-2 infection occurring from Screening and prior to the end of immunogenicity assessments will be removed from applicable immunogenicity analyses as defined in the SAP.

- Any acute illness (cardiovascular, endocrine, gastrointestinal, hepatic, renal, neurological, respiratory, or other medical disorders) that is actively causing symptoms that could, in the opinion of the investigator, impact the assessment of reactogenicity or other study assessments may have planned study vaccination deferred for a later date, but these criteria are not exclusionary for study enrolment. Participant may be vaccinated once symptoms have resolved or are stabilised for > 3 days. Out-of-window study vaccination is allowed for this reason.
- Any participant who is otherwise eligible with a blood pressure of ≥ 160/100 mmHg may be retested onsite several times over a 3-hour interval to achieve a lower blood pressure. If the blood pressure remains ≥ 160/100 mmHg, study vaccination should be deferred for a later date if the baseline blood pressure is found to be < 160/100 mmHg.

4.4 Withdrawal of Participants from the Study

4.4.1 Reasons for Withdrawal

Participants can withdraw consent and discontinue from the study at any time, for any reason. Participants may refuse further procedures (including study vaccination) but are encouraged to remain in the study for safety follow-up. In such cases where only safety is being conducted, participant contact could be managed via telemedicine contact (e.g., telephone, web chat, video, FaceTime).

The investigator will **withhold** further study vaccination from a participant in the study if the participant:

- 1. Is noncompliant with the protocol.
- 2. Experiences an SAE or intolerable AE(s) for which study vaccination is not advised by the investigator.
- 3. Becomes pregnant (discontinuation of further study vaccination required).

The investigator can also withdraw a participant upon the request of the sponsor or if the sponsor terminates the study.

4.4.2 Handling of Withdrawals

Participants are free to withdraw from the study at any time upon request. Participant participation in the study may be stopped at any time at the discretion of the investigator or at the request of the sponsor.

When a participant withdraws from the study, the reason(s) for withdrawal shall be recorded by the investigator on the relevant page of the electronic case report form (eCRF). Whenever possible, any participant who withdraws from the study prematurely will undergo all end of study (EOS) assessments. Any participant who fails to return for final assessments will be SARS-CoV-2 rS Vaccine Novavax, Inc.

contacted by the site in an attempt to have them comply with the protocol. The status of participants who fail to complete final assessments will be documented in the eCRF.

4.4.3 Replacements

Participants who withdraw, are withdrawn or terminated from this study, or are lost to follow-up after signing the informed consent form (ICF) but prior to first study vaccination may be replaced. Participants who receive study vaccine and subsequently withdraw, are discontinued from further study vaccination, are terminated from the study, or are lost to follow-up will not be replaced.

5. TEST ARTICLES

5.1 Study Vaccines Administered

Study vaccinations (SARS-CoV-2 rS with Matrix-M1 adjuvant or placebo) will comprise 2 IM injections (Day 0 and Day 21), ideally in alternating deltoids. For blinding purposes, all participants will be vaccinated using the same injection volume (i.e., 0.5 mL). The dose level will be 5 µg SARS-CoV-2 rS with 50 µg Matrix-M1 adjuvant (co-formulated in a single vial); placebo will be saline for injection. Study vaccinations will be administered on an outpatient basis by designated site personnel in a way to maintain the blind. Any pharmacy preparation with unblinded product will require unblinded site personnel who will not otherwise be involved in the study procedures or observation of participants.

The seasonal influenza vaccine co-administration sub-study will comprise a single IM injection (0.5 mL) of a licensed influenza vaccine on Day 0, ideally in the opposite deltoid of the study vaccine. Seasonal influenza vaccine will be administered in an open-label manner. Flucelvax Quadrivalent will be given to those 18 to 64 years of age, and an adjuvanted trivalent influenza vaccine will be given to those ≥ 65 years of age.

Whenever possible the RIGHT deltoid will be used for the influenza vaccine and the LEFT deltoid for the study vaccine.

5.2 Investigational Products

Supplied Formulation			
Solution for preparation for injection, at a concentration of 5 μ g antigen and 50 μ g adjuvant.			
Sodium chloride injection (BP, sterile), 0.9%			
ion Sub-Study			
Single-dose pre-filled syringe (0.5 mL) or multi-dose vial			
Adjuvanted trivalent seasonal influenza vaccine Single-dose pre-filled syringe (0.5 mL)			

The following supplies will be used for vaccination in the study:

It is anticipated that the product will be available in a co-formulated single vial.

Further details on the study vaccine can be found in the SARS-CoV-2 rS IB.

5.2.1 Investigational Product Packaging and Storage

Novavax, Inc., will provide adequate quantities and appropriate labelling of SARS-CoV-2 rS with Matrix-M1 adjuvant and PPD will ensure distribution to the clinical sites from a designated depot. Sodium chloride injection (British Pharmacopoeia, sterile) and licensed seasonal influenza vaccine are commercially available and will be supplied by PPD. The clinical unit pharmacy will prepare the study vaccines for each participant. Detailed instructions for the preparation of study vaccine will be provided in a separate pharmacy manual.

All investigational products must be stored according to the labelled instructions in a secure cabinet or room with access restricted to necessary clinic personnel. The site will be required to keep a temperature log to establish a record of compliance with storage conditions.

5.2.2 Investigational Product Accountability

The investigator (or delegate) will maintain accurate records of receipt of all investigational product, including dates of receipt. Accurate records will be kept regarding when and how much investigational product is dispensed and used by each participant in the study. Reasons for departure from the expected dispensing regimen must also be recorded. At the completion of the study, and to satisfy regulatory requirements regarding investigational product accountability, all investigational product will be reconciled and retained or destroyed according to applicable regulations. No investigational product will be destroyed until authorised in writing by the sponsor.

5.3 Method of Assigning Participants to Study Vaccine Groups

Participants will be randomly assigned in a blinded manner using the centralised Interactive Response Technology (IRT) according to pre-generated randomisation schedules. Participants will be randomised in a 1:1 ratio via block randomisation to receive 2 IM injections of the SARS-CoV-2 rS with Matrix-M1 adjuvant or placebo. Randomisation will be stratified by site and by age ≥ 65 years. The first approximately 400 participants who qualify for the seasonal influenza vaccine co-administration sub-study (which may be at select study locations only) will be assigned prior to randomisation. These participants will be part of the solicited AE safety subset analysis. Details regarding the IRT process will be provided separately to the sites.

5.3.1 Blinding Procedures

This is an observer-blinded study. To maintain the blind, placebo vaccination via IM route will be included and unblinded site personnel will manage study vaccine logistics, preparation, and administration so as to maintain the blind from the remainder of the site personnel and participants. The unblinded site personnel will not be involved in study-related

assessments or have participant contact for data collection following study vaccine administration.

Seasonal influenza vaccine will be administered in an open-label manner.

5.3.2 Breaking the Blind

A participant's study vaccine assignment will not be broken until the end of the study for the clinical site study team unless medical treatment of the participant depends on knowing the study vaccine the participant received. In the event that the blind needs to be broken because of a medical emergency, the investigator may unblind an individual participant's study vaccine allocation.

Whenever possible, the investigator should contact the medical monitor to discuss the medical emergency and the reason for revealing the actual study vaccine received by that participant. In the event that the investigator cannot contact the medical monitor in a timely manner the blind may be broken by the investigator. The medical monitor should be contacted as soon as feasible after the unblinding. The study vaccine assignment will be unblinded through IRT. Reasons for study vaccine unblinding must be clearly explained and justified in the eCRF. The date on which the code was broken together with the identity of the person responsible must also be documented.

In the event that a safe and effective vaccine against SARS-CoV-2 is licensed and made widely available during the course of the study, a discussion with appropriate regulatory agencies will take place to discuss if the blind should be broken to offer vaccine to placebo participants.

The blind may also be broken in the event of a Suspected Unexpected Serious Adverse Reaction (SUSAR) to determine regulatory reporting.

In addition to the aforementioned situations where the blind may be broken, the data will also be unblinded to a statistical team at specified time points for planned analyses prior to study completion, as outlined in Section 7.6.

5.4 Study Vaccine Compliance

All doses of the study vaccine should be administered in the clinical unit under direct observation of clinic personnel and recorded in the eCRF. Clinic personnel will confirm that the participant has received the entire dose.

The location (right or left arm), date, and timing of all doses of study vaccine will be recorded in the participants' eCRF. If a participant is not administered study vaccine, the reason for the missed dose will be recorded.

5.5 Concomitant Medications and Prohibitive Therapy

5.5.1 Concomitant Medications

Administration of medications, therapies, or vaccines will be recorded in the eCRF. Concomitant medications will include all medications (including vaccines) taken by the participant from the time of signing the ICF through EOS (or through the early termination visit if prior to that time). Prescription and over-the-counter (OTC) drugs, as well as herbals, vitamins, and supplements, will be included.

5.5.2 **Prohibitive Therapy**

- No live vaccine will be allowed within 4 weeks of first study vaccination until 28 days after second study vaccination (Day 49).
- No vaccine (except for a licensed seasonal influenza vaccine and participants in the seasonal influenza co-administration sub-study) will be allowed within 2 weeks of first study vaccination until 28 days after second study vaccination (Day 49).

No influenza vaccine (except participants in the seasonal influenza co-administration sub-study) will be allowed 7 days before each vaccination.

NOTE: Participants in the seasonal influenza co-administration sub-study will be allowed to have the co-administration of a licensed seasonal influenza vaccine at the same time as first study vaccination.

- No unlicensed vaccine should be given within 45 days prior to first study vaccination until after the last study visit.
- No investigational product (drug/biologic/device) within 45 days prior to first study vaccination until after the last study visit.
- No chronic administration (defined as more than 14 continuous days) of any immunosuppressant medication within 3 months of first study vaccination until the last study visit (except topical steroids or short-term oral steroids with course lasting ≤ 14 days). The use of topical, inhaled, and nasal glucocorticoids will be permitted if other chronic disease conditions are not exclusionary.
- No continuous use of anticoagulants, such as coumarins and related anticoagulants (i.e., warfarin) or novel oral anticoagulants/anti-platelet agents. Use of ≤ 325 mg of aspirin per day as prophylaxis is permitted.

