3.1 Study Vaccination Pause Rules

Study vaccination pause rules based on reactogenicity, AEs, and SAEs related to study participation will be in place to monitor participant safety during the study.

AEs meeting any one of the following criteria will result in a hold being placed on subsequent study vaccinations pending further review by the SMC at the direction of the SMC chair:

• Any toxicity grade 3 or higher (severe or potentially life-threatening) solicited (local or systemic) single AE term occurring in ≥ 10% of participants (after a minimum of 100 subjects are enroled) in the SARS-CoV-2 rS with Matrix-M1 adjuvant group within the first 7 days after study vaccination.

• Any severe unsolicited single AE preferred term for which the investigator assesses as related that occurs in ≥ 5% of participants (after a minimum of 100 subjects are enroled) in the SARS-CoV-2 rS with Matrix-M1 adjuvant group, within the first 7 days after study vaccination.

In addition, any SAE assessed as related to vaccine (final assessment by the sponsor) will be reported by the sponsor to the SMC Chair as soon as possible, and within 24 hours of the sponsor's awareness of the event. Based on this initial report of the event to the SMC Chair, the Chair may advise the sponsor to immediately pause enrolment and further dosing in either some or all subjects in the study and to convene an ad hoc meeting, or make alternative recommendations. The SMC Charter defines processes for how this review will occur and how the Chair's recommendations will be documented.

The sponsor, along with medical monitor, may request an SMC review for any safety concerns that may arise in the study, even if they are not associated with any specific pause rule; for example, any SAE for which causality is at least possibly related.

The 400 subject influenza vaccine co-administration study will utilize the same pause rules with one difference due to the expectation of greater reactogenicity and the small size:

Any grade 3 or higher (severe or potentially life-threatening) solicited (local or systemic) single AE term occurring in ≥ 20% of participants in the SARS-CoV-2 rS with Matrix-M1 adjuvant plus seasonal influenza vaccine group, within the first 7 days after study vaccination.

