- 14. Study team member or first-degree relative of any study team member (inclusive of sponsor, contract research organisation (CRO), and site personnel involved in the study).
- 15. Participants who are having any current workup of undiagnosed illness within the last 8 weeks that is either participant-reported or has been clinician-assessed, which could lead to a new condition or diagnosis.
- 16. Received any live vaccine within 4 weeks or **any vaccine** (excluding influenza) within 2 weeks prior to first study vaccination or any licensed influenza vaccine within 1 week prior to first study vaccination or plans to receive any vaccine from these time periods until 28 days after second study vaccination.

NOTE: An influenza co-administration sub-study will occur in which 400 participants will receive a single dose of seasonal influenza vaccine at the same time as first study vaccination. In addition, a licensed seasonal influenza vaccine may be given 7 days after each vaccination but should not be given within 7 days prior to second vaccination.

- 17. Have clinically significant chronic cardiovascular, endocrine, gastrointestinal, hepatic (including hepatitis B and C), renal, neurological, respiratory, psychiatric or other medical disorders not excluded by other exclusion criteria, that are assessed by the investigator as being clinically unstable within the prior 4 weeks as evidenced by:
 - a. Hospitalisation for the condition, including day surgical interventions.
 - b. New significant organ function deterioration.
 - c. Needing addition of new treatments or major dose adjustments of current treatments (mild or moderate well-controlled comorbidities are allowed).
- 18. History of chronic neurological disorders that have required prior specialist physician review for diagnosis and management (such as multiple sclerosis, dementia, transient ischemic attacks, Parkinson's disease, degenerative neurological conditions, and neuropathy) or a history of stroke or previous neurological disorder within 12 months with residual symptoms. Participants with a history of migraine or chronic headaches or nerve root compression that have been stable on treatment for the last 4 weeks are not excluded.
- 19. Any autoimmune disease/condition (iatrogenic or congenital) listed in Table 9-3 or being treated with a biologic therapy.

NOTE: The Skin and Metabolic Disorders listed in Table 9-3 are eligible at the discretion of the investigator.

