7.3.3 Safety Analyses

Solicited AEs (e.g., local and general systemic reactogenicity symptoms) will be captured in the Safety Subset of approximately 2,000 participants and in the seasonal influenza vaccine co-administration sub-study of approximately 400 participants.

Numbers and percentages (with 95% CIs based on the Clopper-Pearson method) of participants with solicited local and systemic AEs through 7 days after each study vaccination will be summarised by study vaccine group and the maximum toxicity grade over 7 days after each study vaccination. The duration of solicited local and systemic AEs after each study vaccination will also be summarised by treatment group.

Unsolicited AEs will be coded by preferred term and system organ class using the latest version of the MedDRA and summarised by study vaccine group as well as by severity and relationship to study vaccine. AEs through 49 days after first study vaccination; all MAAEs

through 35 days after first study vaccination; and MAAEs related to study vaccine; SAEs; or AESI through EOS will be listed separately and summarised by study vaccine group.

Vital sign measurements will be summarised by study vaccine group using descriptive statistics at baseline and following study vaccination.

Concomitant medications will be provided in a data listing with preferred drug name as coded using the World Health Organisation drug dictionary.

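### Section 5.5.2 sets no influenza-vaccine interval after a study dose, while the NOTE to exclusion 16 implies one of 7 days; the two texts disagree on days inside the solicited-AE windows

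*Protocol*

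**What the plan says.** Three pieces of protocol text govern influenza vaccination of participants outside the roughly 400-person co-administration sub-study.

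- **Exclusion 16, main text (Section 4.2, repeated in the synopsis).** It excludes anyone who "plans to receive any vaccine from these time periods until 28 days after second study vaccination". This clause makes no exception for influenza vaccine.
- **NOTE to exclusion 16 (same places).** It says that "a licensed seasonal influenza vaccine may be given 7 days after each vaccination" but that it "should not be given within 7 days prior to second vaccination".
- **Section 5.5.2, Prohibitive Therapy.** The general ban, which runs to Day 49, reads in part: "No vaccine (except for a licensed seasonal influenza vaccine and participants in the seasonal influenza co-administration sub-study) will be allowed within 2 weeks". The only influenza-specific rule is: "No influenza vaccine (except participants in the seasonal influenza co-administration sub-study) will be allowed 7 days before each vaccination". A separate bullet bars any live vaccine to Day 49.

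For the safety data, Section 6.4.1.1.2 collects solicited AEs from each study vaccination until 7 days after it, in a Safety Subset of about 2,000 and in the sub-study. Section 6.4.1.5 treats solicited reactions as related to study vaccination. Section 7.3.3 reports numbers and percentages of "participants with solicited local and systemic AEs through 7 days after each study vaccination will be summarised by study vaccine group". Section 3.1 sets a 10% pause threshold for any single solicited AE term of grade 3 or higher in the vaccine group. It sets 20% for the influenza sub-study, "due to the expectation of greater reactogenicity and the small size".

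**The concern.** Sites apply eligibility and prohibited-therapy rules directly, so the protocol has to give one answer. Take a Safety Subset participant who has an influenza vaccination two days after dose 1. Section 5.5.2 on its own places no bar on it. The NOTE implies that it is too early. The main text of exclusion 16, read alone, would have excluded a participant who planned it.

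The situation is foreseeable: Section 3 says that the study enrols during the influenza season, and it targets at least 25% of participants aged 65 or over.

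The statistical consequence is misattribution. A systemic reaction to the influenza vaccine in those days would be recorded as a solicited AE, classed as related to the study injection, and summarised under the assigned group. Section 6.4.1.1.2 says that local symptoms at the influenza injection site are not to be recorded, so the exposure is mainly in the systemic terms. Such a participant might also count toward the 10% pause threshold, and the protocol does not say whether that is intended. Finally, whether the vaccination is a protocol deviation depends on which section is read.

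**Working it through.** No power, alpha or event count is involved, and the plan states no figure to reproduce. The check is a day count.

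**Inputs.** Doses are on Day 0 and Day 21, with a +7-day window for the second (Sections 3 and 5.1). The solicited window runs from the dose to 7 days after it (Section 6.4.1.1.2). The vaccine is a non-live licensed seasonal influenza vaccine, and the participant is outside the sub-study. An influenza vaccination on the day of a dose is taken as following the dose. The NOTE's wording is read as opening the permission on the seventh day after the dose.

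| | Dose 2 on Day 21 | Dose 2 on Day 28 |
|---|---|---|
| Open under Section 5.5.2 | Days 0-13, and from Day 21 | Days 0-20, and from Day 28 |
| Open under the NOTE | Days 7-13, and from Day 28 | Days 7-20, and from Day 35 |
| Barred by both | Days 14-20 | Days 21-27 |
| **Texts disagree** | **Days 0-6 and 21-27** | **Days 0-6 and 28-34** |
| Solicited-AE windows | Days 0-7 and 21-28 | Days 0-7 and 28-35 |

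**Result.** The disagreement covers 7 + 7 = 14 days, all inside the solicited windows, which span 8 + 8 = 16 calendar days. Under Section 5.5.2 both windows are fully open. Under the NOTE only the boundary day of each window (Day 7, and Day 28 or 35) is open. The two texts agree on the 7 days before dose 2.

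**Main text of exclusion 16.** Its clause on planned vaccines runs to 28 days after dose 2, that is 21 + 28 = Day 49. Section 5.5.2 exempts licensed influenza vaccine from its ban over that period, and the NOTE permits it from the seventh day after each dose. The main text therefore lacks an exception that both other texts take for granted.

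**Size of the effect on rates.** The shift in an arm's solicited-AE rate is the share of participants given influenza vaccine in the window, multiplied by the added reaction rate. The protocol gives neither quantity, so no numerical shift can be derived from it.

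**The case against.** The strongest reply is that this is a wording gap that a careful site can resolve. The NOTE sits directly under exclusion 16 and qualifies it, Section 5.5.2 agrees with the NOTE that influenza vaccine is allowed before Day 49, and following the NOTE satisfies both. The NOTE's post-dose gap is also only implied by permissive wording. Much of this stands: the core is a conflict between two texts, with a missing exception in a third. But a permission that starts at 7 days has little purpose if earlier days are open too, and Section 5.5.2 is the place where a site would look for the rule after enrolment.

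Several stronger readings are tempting and not supported:

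- **Older and comorbid participants would be turned away.** This requires reading exclusion 16 without its own NOTE.
- **Early influenza vaccination would be no deviation.** Section 9.3.3.2.2 defines a deviation as a departure from procedures in the protocol, and the NOTE is protocol text. The status is unclear rather than settled.
- **The case is common.** Winter enrolment and the age target make it foreseeable but give no frequency. Some participants may already be vaccinated, and the first 400 or so who qualify enter the sub-study.
- **Arm rates move by a stated amount.** Assuming 5-20% uptake and 10-20 added percentage points gives 0.05 × 10 = 0.5 to 0.20 × 20 = 4 points, but nothing in the protocol anchors either input.
- **The comparison between arms is biased.** Under blinded 1:1 randomisation, influenza vaccination should be similar in both arms, so the contrast is largely preserved.
- **The pause rule is shown to be distorted.** It counts single terms of grade 3 or higher. The expectation of greater reactogenicity in Section 3.1 concerns same-day co-administration, and no effect on the count can be calculated.

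Live influenza vaccine remains barred by Section 5.5.2, so it is outside the conflict.

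**Conclusion.** The contradiction holds on the text. Section 5.5.2 and the NOTE to exclusion 16 give different answers for non-live influenza vaccine on Days 0-6 and 21-27 (dose 2 on Day 21), all within the solicited-AE windows. The main text of exclusion 16 is out of step with both. This rests on reading the NOTE's permission as starting on the seventh day after a dose.

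The consequences are limited to absolute solicited-AE rates in the Safety Subset, possibly the reactogenicity pause count, and the classification of deviations. The primary efficacy analysis is largely unaffected. The frequency is unknown. The point deserves correction because sites apply these rules directly and the correction is cheap; it does not threaten the trial's main conclusion.

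**What to change.** 1. Reconcile the main text of exclusion 16, its NOTE (in Section 4.2 and the synopsis) and Section 5.5.2 into one statement of when influenza vaccine is allowed before and after each study dose. The interval is the sponsor's choice. If influenza vaccine is meant to be allowed, except it explicitly from the clause on planned vaccines.
2. Use the concomitant-vaccine dates already recorded under Section 5.5.1 to flag Safety Subset participants given influenza vaccine within 7 days after a study dose. Add a supportive solicited-AE summary that excludes those doses, and leave the main summary as planned.
3. Leave the pause-rule count as it is, and ask the sponsor only to state whether such participants count toward the 10% threshold.

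The cost is a wording change in each of these places, one derived flag and one supportive table, with no new data collection. The supportive summary will have a slightly smaller denominator.
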